8.7.4 Treatment for Surgery or Dental Procedures

Subjects enrolled in this continuation study who require elective major or minor surgical or dental procedures or minor emergency surgical or dental procedures may be eligible to enroll in the BAX 855 surgery study (Study 261204), which is evaluating efficacy and safety of BAX 855 for perioperative management, if the study is open for enrollment. Exemptions may be granted for minor interventions in case the surgery study is not in place at the study site and the intervention can be managed by one prophylactic infusion and an additional infusion to maintain hemostasis. However, to ensure an adequate dose, at least an individual IR must be available which can also be based on FVIII activity levels determined at the local laboratory with back-up samples drawn for determination at the central laboratory. Any required major emergency surgery will result in withdrawal of the subject.

Upon completion of the surgery study, subjects may be eligible to return to this continuation study when they are able to resume their continuation study-specific prophylaxis regimen and with the approval of the sponsor's medical director. Upon return to this study, these subjects will receive their previous continuation study treatment regimen.

Subjects from this continuation study who participate in the surgery study will continue to receive their study-specific BAX 855 treatment from the continuation study as follows:

- For subjects undergoing PK (required for major surgery) or IR (required for minor surgery) assessment in the surgery study:
 1. From signing the informed consent until the pre-surgical PK^{vi}/IR^{vii} assessment required for major surgery.
 2. From completion of the pre-surgical PK/IR assessment until the loading dose prior to surgery.
- For subjects not undergoing PK/IR assessment in the surgery study:
 1. From signing the informed consent until the loading dose prior to surgery.

During the period from screening up to the loading dose prior to the surgery in which subjects receive BAX 855 from the continuation study, subjects will maintain their e-diaries for the continuation study, and the investigator of the continuation study will be responsible for the subject's safety and treatment. Any data collected during the above-listed periods will be recorded as part of this continuation study.

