10.4 Medications and Non-Drug Therapies

The following medications are **not** permitted within 30 days before study entry and during the course of the study:

- Any PEGylated medication (eg, PEG-interferon)
- Any investigational drug, biologic, or device, except BAX 855 in case of transitioning subjects

A subject who has taken any of these medications will be considered a protocol deviation.

The use of any FVIII concentrate other than BAX 855 during the course of the study following the first BAX 855 infusion^{xii} will result in the immediate withdrawal of the subject. Every effort should be made to have the Completion/Termination Visit performed. The use of (commercial) ADVATE may be permitted for a short period of time for administrative reasons.

The following medications and non-drug therapies are permitted before study entry and during the course of the study:

- Medications:
 - Hemostatic agents, such as tranexamic acid, are permitted, as indicated by the subject's treating physician, to treat mucosal bleeding during the study
 - Any medications deemed necessary by the subject's physician to treat or prevent any medical condition
 - Any over-the-counter medication used by the subject to treat symptoms or signs
 - Supplemental vitamins, minerals
- Non-drug therapies:
 - Any non-drug therapy (eg, physiotherapy) deemed necessary by the subject's physician to treat or prevent any medical condition

^{xii} This infusion may be the first prophylactic infusion or infusion for the determination of IR for FVIII activity.

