10.6 Subject Completion/Discontinuation

A subject is considered to have completed the study when he/she ceases active participation in the study because the subject has, or is presumed to have, completed all study procedures according with the protocol (with or without protocol deviations).

Reasons for completion/discontinuation will be reported on the Completion/Discontinuation eCRF, including: completed, screen failure, AE (eg, death), discontinuation by subject (eg, lost to follow-up [defined as 3 documented unsuccessful attempts to contact the subject], dropout), physician decision (eg, pregnancy, progressive disease, non-compliance with IP/protocol violation(s)), study terminated by sponsor, or other (reason to be specified by the investigator, eg, technical problems). Regardless of the reason, all data available for the subject up to the time of completion/discontinuation should be recorded in the appropriate eCRF.

Every effort will be made to have discontinued subjects complete the study completion/termination visit. If the completion/termination visit is done as an additional, unscheduled visit, the assessment results shall be recorded with the completion/termination visit. If a subject terminates participation in the study and does not return for the completion/termination visit, their last recorded assessments shall remain recorded with their last visit. The reason for discontinuation will be recorded, and the data collected up to the time of discontinuation will be used in the analysis and included in the clinical study report. If additional assessments are required, the assessments shall be recorded separately. Assessments to be performed at the termination visit (including in cases of withdraw or discontinuation) can be found in Supplement 20.3 Schedule of Study Procedures and Assessments and Supplement 20.4 Clinical Laboratory Assessments.

In the event of subject discontinuation due to an AE, clinical and/or laboratory investigations that are beyond the scope of the required study observations/assessments may be performed as part of the evaluation of the event. These investigations will take

place under the direction of the investigator in consultation with the sponsor, and the details of the outcome may be reported to the appropriate regulatory authorities by the sponsor.

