## 6.7 Extent of Exposure

The following information is to be obtained from the eCRF:

- Information on study infusions (*Study Infusions* eCRF panels).
- Treatment regimen, including planned dose (*Treatment Assignment* and *Change of Treatment Assignment* eCRF panels).
- Body weight (*Vital Signs* eCRF panels).

The following derivations based on eCRF reported results are to be performed:

- Body weight-adjusted dose (IU/kg) is to be derived as the total units infused (IU) divided by the last available body weight (kg) prior to the infusion. Refer to Section 5.4: Handling of Missing, Unused, and Spurious Data for imputation schemes to be implemented.
- Total number of infusions in this study are determined as the count of the number of infusions, regardless of date and time, the subject had. Number of infusions are to be determined overall and by reason for infusion as well as by the treatment regimen assigned to at the time of receiving the treatment.
- The number of EDs are determined as the number of unique calendar days on which a subject received any or part of any infusion. Multiple infusions on the same day are still to be considered one ED. EDs are to be determined overall as well as for each reason an infusion is given. The number of EDs will be determined for this study and across all previous BAX 855 studies the subject participated in. EDs in this study will be derived as the number of infusions on unique calendar days in this study, while EDs from previous BAX 855 studies will be obtained as reported in the eCRF. The total EDs across all BAX 855 studies will be determined as the sum of EDs in current study and EDs in previous studies.
- The observation period for efficacy (OPE) in days in the study for subjects who never transferred to the surgery study is to be determined as:

$$OPE(Days) = (Stop\ Date - Start\ Date) + 1$$
 where "Start Date" refer to the first BAX 855 infusion in the current study and "Stop Date" to the last BAX 855 infusion in the current study. For subjects on the PK-guided regimen, first BAX 855 infusion will be the first prophylactic infusion.

• The OPE in days for subjects that did transfer to the surgery study is to be determined as:

$$OPE(Days)$$

$$= (Date\ of\ Transfer\ to\ Surgery\ Study - Start\ Date) + (Stop\ Date - Return\ Date\ to\ Current\ Study) + 1$$
where "Start\ Date" and "Stop\ Date" are\ defined\ as\ above.

• The OPE in weeks is to be determined from the OPE in days as:

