- A bleed is considered to be a minor bleed if the severity is indicated as "Mild" or "Minor".
- A bleed is considered to be a weekday bleed if the bleed occurred on a Monday, Tuesday, Wednesday, Thursday or Friday.
- A bleed is considered to be a weekend bleed if the bleed occurred on a Saturday or Sunday.
- A bleed is considered to be a morning bleed if the bleed occurred between 04:00 and 11:59.
- A bleed is considered to be an afternoon bleed if the bleed occurred between 12:00 to 17:59.
- A bleed is considered to be a night bleed if the bleed occurred between 18:00 and 03:59.
- A bleed is considered to have occurred at an unknown time if the time of a bleed is not available.
- Time since last prophylactic infusion in hours is to be derived as:
  - $Time(h) = Date/Time\ of\ Bleed\ Start\ Date/Time\ of\ Infusion$  where the start date/time of infusion refers to the last prophylactic infusion received (other than to treat a bleed) prior to the start of the bleed. Time since last prophylactic dose is to be categorized as:
    - $\circ$  <24 hours.

```
24 - <48 hours.

48 - <72 hours.

72 - <96 hours.

>96 hours.
```

• Time since previous bleed are only to be determine if a subject had multiple bleeds and is to be derived as:

```
Time(months)
= (Date/Time \ of \ Current \ Bleed
- Date/Time \ of \ Previous \ Bleed)/365.2425 \times 12
```

- A bleed is considered to be treated with BAX 855 if at least one infusion linked to the particular bleed is present in the *Study Infusion* eCRF panels. Infusions to "Maintain Hemostasis" are not to be summarized as part of treatment for bleeding episodes.
- The number of bleeds per subject overall and by location (target joint, non-target joint, joint and non-joint), causality (spontaneous/unknown and injury), severity (mild, moderate and severe) and timing (weekends, weekdays, morning, evening and afternoon) are to be determined as the count of unique bleeds in each category a subject had during the observation period.
- Annualized bleeding rate (ABR) is to be derived for each treatment regimen the subject had during the study as:

$$ABR = \frac{Number\ of\ unique\ bleeds}{OPE\ (years)\ for\ treatment\ regimen}$$

The ABR is to be analyzed using a generalized linear model fitting a negative binomial distribution with logarithmic link function. Only subjects that have 100 or more EDs are to be included in the models, where total EDs are derived as in Section 6.7: Extent of Exposure.

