The model is to be analyzed separately for each of the every 5 days and every 7 days treatment regimen. Baseline age and ABR as continuous covariate and the logarithm of the OPE in years, specific to each treatment regimen, as an offset, is to be included in the model. The following SAS® code is to be used to perform the analysis:

```
PROC GENMOD DATA = <ds>;
   MODEL <bleds> = <baseline_age> <baseline_ABR> / DIST = NEGBIN
   OFFSET = <log_OPE> LINK = LOG;
   LSMEANS <regimen> / BYLEVEL OM CL;
   ODS OUTPUT LSMEANS = <outds>;
RUN;
QUIT;
```

where <ds> refers to the input dataset, <regimen> the particular treatment regimen time of bleed, <ble> the number of bleeds during the observation period, 
 baseline\_age> the age at baseline, 
 baseline\_ABR> the ABR at baseline and <log\_OPE> the logarithm of the OPE in years, specific to the treatment regimen. Point estimates and confidence intervals obtained from the generalized linear model are to be anti-logged prior to presentation.

The twice weekly regimen and PK-tailored regimen will be analyzed together (not separately as per above model) using a generalized estimating equation (GEE) model using the following SAS® code:

```
PROC GENMOD DATA = <ds>;
   CLASS <subject> <regimen>;
   MODEL <bleeds> = <regimen> <baseline_age> / DIST = NEGBIN
   OFFSET = <log_OPE> LINK = LOG;
   REPEATED SUBJECT = <subject> / CORR = EXCH;
   LSMEANS <regimen> / BYLEVEL OM CL;
   ODS OUTPUT LSMEANS = <outds>;
RUN;
```

where <ds>, <regimen>, <bleeds>, <baseline\_age> and <log\_OPE> is define the same as before and <subject> is the subject number.

For both models above, should the model not converge a poisson model will be fitted instead. Should the non-convergence be due to all bleeds equal to zero, the estimate will be presented as zero with no confidence interval.

The model results are to be presented on the FAS and PPAS for:

- The total ABR.
- Annualized joint bleeding rate.
- Annualized non-joint bleeding rate.
- Annualized target joint bleeding rate.
- Annualized non-target joint bleeding rate.
- Annualized injury related bleeding rate.
- Annualized spontaneous/unknown bleeding rate.
- Annualized severe bleeding rate.
- Annualized moderate bleeding rate.
- Annualized minor bleeding rate.
- Annualized weekday bleeding rate.

- Annualized weekend bleeding rate.
- Annualized morning bleeding rate.
- Annualized afternoon bleeding rate.
- Annualized night bleeding rate.
- Annualized bleeding rate at unknown time.

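### Ending the efficacy period at the last BAX 855 infusion drops a final bleed from the primary and secondary ABR when a subject leaves with no later counted BAX 855 infusion

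*SAP*

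**What the plan says.** SAP 6.7 (Extent of Exposure) computes the OPE as stop date minus start date plus one day. The stop date refers "to the last BAX 855 infusion in the current study". OPE is derived overall and per treatment regimen.

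SAP 7.1 (Bleeding Episodes) derives the number of bleeds "as the count of unique bleeds in each category a subject had during the observation period", and ABR is that number divided by the OPE in years. The response in the ABR models is likewise "the number of bleeds during the observation period", with the log of OPE as offset. The models are restricted: "Only subjects that have 100 or more EDs are to be included in the models".

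The protocol takes a wider view:

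- Section 11.1 defines a bleeding episode whether or not FVIII treatment is needed.
- Section 13.4.1.2 uses follow-up time, not an infusion-to-infusion period, as the offset.
- Section 10.6 states that "the data collected up to the time of discontinuation will be used in the analysis".

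The protocol also names events that end participation. Under 10.4, use of another FVIII concentrate after the first BAX 855 infusion "will result in the immediate withdrawal of the subject", apart from short administrative use of ADVATE. Under 8.7.4: "Any required major emergency surgery will result in withdrawal of the subject". Section 9.3 adds life-threatening bleeds, and severe trauma or emergency surgery managed with other FVIII, as possible reasons.

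**The concern.** A bleed after the last BAX 855 infusion lies outside the OPE, so it reaches neither the descriptive nor the modelled ABR. Cutting follow-up short does no harm in itself if time and events are cut alike and the cut is unrelated to bleeding. Here the cut can be caused by the bleed: a subject treated elsewhere with another product, or who stops because of the bleed, may never receive BAX 855 again. One event is then lost and only a few days of time with it.

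The SAP's own compliance rule makes the gap visible. SAP 6.8 regards a subject as still exposed for up to 5 days after an infusion on the twice-weekly and every-5-day regimens, and up to 7 days on the every-7-day regimen. Days that count as exposed for compliance are thus not observed for efficacy.

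At stake are the co-primary spontaneous ABR, the total ABR and the severe-bleed rate, which SAP 7.1 models separately. SAP 5.7, which lists departures from the protocol's analysis, does not mention the stop date.

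**Working it through.** The documents state no figure on this point, so there is none to reproduce. The check applies the SAP's formulas to assumed cases.

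**Formulas (SAP 6.7 and 7.1).** OPE in days = stop − start + 1; OPE in years = days / 365.2425; ABR = unique bleeds / OPE in years.

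**1. One subject.** Follow-up of 3, 6 and 12 months is taken from the planned range of about 3 to 12 months in Protocol 8.3. Assumptions: last BAX 855 infusion 4 days before last contact; a final bleed one day before last contact, not treated with BAX 855; no end-of-study infusion.

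| Last contact (day) | OPE under SAP (days) | Earlier bleeds | ABR under SAP | ABR with OPE to last contact |
|---|---|---|---|---|
| 91 | 87 | 0 | 0.00 | 1/(91/365.2425) = 4.01 |
| 183 | 179 | 0 | 0.00 | 1/(183/365.2425) = 2.00 |
| 365 | 361 | 0 | 0.00 | 1/(365/365.2425) = 1.00 |
| 183 | 179 | 1 | 1/(179/365.2425) = 2.04 | 2/(183/365.2425) = 3.99 |

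If an end-of-study infusion is given on day 183 and counted, the OPE is 183 days, the day-182 bleed is inside, and the ABR is 2.00 under the SAP as well. The loss therefore depends on that infusion being absent or not counted.

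**2. The cohort.** Assume 250 subject-years and 1.2 spontaneous bleeds per year, so 250 × 1.2 = 300 bleeds counted. If k more are lost, the understatement is k/(300 + k):

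- k = 3: 3/303 = 1.0%
- k = 5: 5/305 = 1.6%
- k = 10: 10/310 = 3.2%

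The result depends on the assumed bleed total. With 200 subjects, half a year each and a true ABR of 1 (100 bleeds), losing 5 lowers the rate by 5%. With one year each and a true ABR of 2 (400 bleeds), losing 5 lowers it by 1.25%. For the models, k counts only bleeds lost in subjects with at least 100 exposure days.

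**3. Severe bleeds.** If 10 major bleeds are counted and all the lost ones are major, the understatement is 3/13 = 23%, 5/15 = 33% or 10/20 = 50%. These show only how sensitive a small count is.

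**4. Does the end-of-study infusion set the stop date?** SAP 4.2 lists the IR infusion panels separately from the Study Infusion panels; SAP 6.7 names only Study Infusions as its infusion source. If the IR infusion is not read, each subject attending the visit loses the preceding washout of 84 to 96 hours, or 3.5 to 4 days. For 250 subjects that is 250 × 3.5/365.2425 = 2.4 to 250 × 4/365.2425 = 2.7 person-years, plus any bleeds in it. Here time and bleeds go together, so the direction of any bias is less clear than in step 1.

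**The case against.** The strongest reply is that the protocol already closes most of the gap. The end-of-study visit for both regimens (20.2.1.4 and 20.2.2.6) includes a BAX 855 infusion for IR, and its procedures also apply at withdrawal or discontinuation. When that infusion is given and counted, every earlier bleed is inside the OPE, whatever treated it. A reader might infer that a final untreated or otherwise-treated bleed always falls outside; the documents do not support that.

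The safeguard is incomplete, however. Sections 10.4 and 10.6 ask only for every effort to hold the visit, and 10.6 provides for subjects who do not return. The visit also requires at least 84 hours since the last BAX 855 dose and no active bleeding.

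Other parts of the reply stand:

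- The models exclude subjects below 100 exposure days, so early leavers affect only the descriptive ABR. Exposure days accumulate across studies and participation may continue past 100 (Protocol 8.3), so later leavers do enter the models.
- Protocol 8.7.3.5 has major bleeds treated with BAX 855; a bleed so treated is inside the OPE.
- Use of another FVIII product need not end participation. Section 10.4 allows short administrative use of ADVATE, SAP 2 notes ADVATE rescue before amendment four, and 9.3 speaks of possible withdrawal after repeated use. Sections 10.4 and 9.3 should be reconciled. A subject who continues on BAX 855 keeps the bleed in the count.
- Precision dominates the overall rate: with 300 bleeds, even a Poisson 95% interval is about ±1.96/√300 = ±11%. The study has no control group, and no between-product test depends on this.

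**Conclusion.** The concern holds for subjects who leave with no later counted BAX 855 infusion. For them the SAP excludes a final bleed that Protocol 11.1 defines as a bleed and 10.6 says will be used, and the ABR is biased downward. The effect on the overall spontaneous ABR is probably small: about 1 to 3% with 300 counted and 3 to 10 lost bleeds, more if follow-up is short and bleeding rare. The severe-bleed rate could move more. All of these rest on assumed counts.

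Three stronger readings are not supported:

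- That such a bleed is missing from every ABR: the exploratory three-month ABR in SAP 10.5 counts bleeds to the next scheduled visit, and SAP 7.1 lists all bleeding episodes.
- That the severe rate is understated by a third: that needs five lost bleeds, all major, against ten counted, and nothing in the documents supplies those numbers.
- That completers are certainly unaffected: this depends on whether the IR infusion sets the stop date, which the SAP leaves open.

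The change is worth making before the analysis because the loss is selective and the remedy needs no new data.

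**What to change.** In SAP 6.7:

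1. End the OPE at the end-of-study or termination visit; if there is none, at the date of discontinuation or last diary contact.
2. Count every bleed with onset up to that date, whatever product, if any, treated it.
3. State that IR infusions count as BAX 855 infusions when dates are set, and name the eCRF panels used.
4. At a change of regimen, end the old regimen's period on the day before the first infusion of the new one, so that time and bleeds are neither lost nor counted twice.
5. List the change in SAP 5.7.

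The cost is one revised derivation on data already collected. Some discontinued subjects will contribute a few days after their last dose has run out, and the ABR may rise slightly.

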#### **6.8** Measurements of Treatment Compliance

Treatment compliance is to be derived using results and derivations obtained from study exposure as described in Section 6.7: Extent of Exposure.

Treatment compliance is to be based on the following:

- Adherence to the infusion schedule; and
- Adherence to recommended prophylactic dose.

An infusion is considered to be in adherence to the infusion schedule if:

- Time since last infusion on the "twice weekly regimen" do not exceed 5 days.
- Time since last infusion on the "every 5 day regimen" do not exceed 5 days.
- Time since last infusion on the "every 7 day regimen" do not exceed 7 days.
- Time since last infusions on the "other dosing regimen" do not exceed the days specified by the investigator.

Based on the treatment regimen, time that a subject was not exposed to BAX 855 is to be determined. Time a subject was not exposed to BAX 855 is to be derived as:

- = Days since last BAX 855 infusion
- Treatment regimen allowed days

Time not exposed (days) is to be set to 0 days if the above derivation results in number of days less than 0. The total time not exposed to BAX 855 for each subject will be determined as the sum of times not exposed for each individual infusion.

The percentage of time a subject was exposed to BAX 855 is to be derived as follows:

$$\textit{Time Exposed (\%)} = \frac{\textit{OPE(Days)} - \textit{Total Time not Exposed (Days)}}{\textit{OPE(Days)}} \times 100$$

An infusion is considered to be in adherence to the recommended prophylactic dose if the actual amount infused (IU/kg) are between 90% and 110% of the planned dose (IU/kg) to be infused. Infusions with actual amount infused not recorded in the eCRF are to be excluded from the compliance calculations.

The number and percentage of infusions in adherence to the recommended prophylactic dose will be determined for each subject and treatment regimen using the overall number of infusions for that subject as denominator.

Treatment compliance are to be summarized for the SAS and PPAS and listed for the SAS. Summaries are to be presented by age category and treatment regimen at time of dose on a subject level.

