8.7.3.1 Fixed Dose Prophylactic Treatment Regimen

The fixed dose prophylactic treatment regimen with BAX 855 will be age-dependent as follows:

- Subjects aged ≥ 12 years: 45 ± 5 IU/kg twice weekly, which may be increased up to 80 IU/kg
- Subjects aged < 12 years: 50 ± 10 IU/kg twice weekly, which may be increased up to 80 IU/kg

Subjects must adhere as closely as possible to the dosing regimen. The days of the week on which treatment is administered may be selected by the subject and/or his/her physician and should be selected to provide maximum coverage for vigorous activities. Dosing must be administered twice weekly, at 3 and 4 day intervals (Option X), or 3.5 day intervals (Option Y with AM and PM dosing) and should be maintained during the study (Table 2). If a dose is missed, it must be documented and the next dose will be taken as soon as possible. After this dose, the regularly scheduled regimen will be resumed. For example, in Option X, if twice weekly dosing is scheduled for every Monday and Thursday and the subject misses the Thursday dose, he/she should infuse the next dose on Friday and then resume his/her schedule with subsequent dose on Monday). And for Option Y, if dosing is scheduled for the morning on Monday and the evening dose on Thursday, and the subject misses the Thursday dose, he/she should infuse the

iv Please note that subjects who are on a 30-80 IU/kg every 5 days (q5d) or every 7 days (q7d) treatment regimen prior to this protocol amendment 4 (dated 23 May 2014) being effective can decide to continue on their 30-80 IU/kg q5d or q7d treatment regimen after this protocol amendment 4 (dated 23 May 2014) is effective. These subjects will then follow the procedures as described for transitioning subjects on a fixed dose prophylactic treatment regimen (see also Supplement 20.3.1). Additionally, these subjects can decide to switch to a fixed dose or PK-tailored prophylactic treatment regimen as per protocol amendment 4 (dated 23 May 2014) at any time during the study.

next dose on Friday morning, and then resume his/her schedule with a subsequent dose on Monday morning.

Table 2 BAX 855 Example Dosing Frequency							
Day	Mon	Tue	Wed	Thu	Fri	Sat	Sun
Morning	X or Y			X			
Evening				Y			

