9.3 Withdrawal and Discontinuation

Any subject may voluntarily withdraw (ie, reduce the degree of participation in the study) consent for continued participation and data collection. The reason for withdrawal will be recorded on the End of Study eCRF. Assessments to be performed at the end of study visit (including in cases of withdrawal or discontinuation) are described in Section 10.6 and Section 20.3.

Discontinuation (ie, complete withdrawal from study participation) may be due to dropout (ie, active discontinuation by subject) or loss to follow-up (ie, discontinuation by subject without notice or action). Additionally, the investigator and sponsor have the discretion to discontinue any subject from the study if, in their judgment, continued participation would pose an unacceptable risk for the subject.

Subjects also may be withdrawn from treatment or discontinued from further study participation for the following reasons:

- The subject develops a confirmed high responder inhibitory antibody to FVIII (>5 BU by Nijmegen modification of the Bethesda assay) or a low responder inhibitory antibody (≤ 5 BU but ≥ 0.6 BU) that cannot be managed by the protocol-required treatment.
- The subject experiences a severe anaphylactic reaction to BAX 855.
- The subject requires therapy with another PEGylated product (eg, PEG-Interferon).
- The subject frequently misses administration of IP (ie, misses more than 30% of planned prophylactic doses within any 3-month period).
- The subject is non-compliant with study procedures, in the opinion of the investigator.

- The subject repeatedly uses another FVIII therapy for prophylaxis (in the absence of an acceptable justification to the sponsor) or for the treatment of bleeding episodes.
- The subject requires a surgical or dental procedure and is not eligible or does not consent for the surgery study, or participates in the surgery study and then refuses to resume participation in this continuation study. If the surgery study is closed, the subject will be withdrawn from the continuation study.
- The subject experiences a life-threatening bleeding episode (eg, any gastrointestinal hemorrhage or intracranial hemorrhage).
- The subject experiences severe trauma or requires emergency surgery with FVIII replacement therapy other than BAX 855.

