#### 4.4 Per Protocol Analysis Set (PPAS)

The per protocol (PPAS) analysis set is to comprise all subjects in the FAS who had no major deviations from the protocol affecting the study results. Protocol deviations are to be obtained from the Clinical Trial Management System (CTMS).

Prior to performing any analysis as set out in this SAP, a meeting is to be held discussing the impact of any major protocol deviation on the analysis. At this meeting, the decision is to be made on whether a subject is to be excluded from the PPAS analysis set or not. The meeting is to be attended by participants from at least Biostatistics and Medical.

Below is a list of possible major deviations that may influence the study results that will be discussed at the analysis set assignment meeting:

- Subject less than 75% exposed to BAX 855 as derived in Section 6.8: Measurements of Treatment Compliance.
- Subject less than 75% compliant to planned dosing regimen.
- More than 10% of treated bleeds have no efficacy rating.
- Use of expired IP.
- Subject did not reach 100 EDs across all BAX 855 studies.
- Use of any FVIII product other than ADVATE, as determined by the medical team.

It should be noted that the above will not necessarily lead to immediate exclusion from the PPAS, but will be discussed prior to locking the database. The database is not allowed to be locked until final approval on the PPAS has been obtained.

During the course of the study, data review meetings are to be held on a regular basis. During these meetings the quality of the data including any potential protocol deviations are to be identified. All protocol deviations identified at these meetings are to be included into the CTMS upon team agreement.

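### SAP 6.8 judges twice-weekly compliance by a 5-day gap limit and never counts infusions given against planned, so a 30% to 36% shortfall in doses can go unflagged

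*SAP*

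**What the plan says.** Protocol 8.7.3.1 sets the twice-weekly schedule: "Dosing must be administered twice weekly, at 3 and 4 day intervals (Option X), or 3.5 day intervals". The longest planned gap is therefore 4 days and the mean is 3.5. On lateness the same section says: "If a dose is missed, it must be documented and the next dose will be taken as soon as possible", after which the usual schedule resumes.

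SAP 6.8 builds compliance from gaps between infusions. For the twice-weekly regimen an infusion is adherent to the schedule if "Time since last infusion on the 'twice weekly regimen' do not exceed 5 days". For the every-5-day regimen the wording is "Time since last infusion on the 'every 5 day regimen' do not exceed 5 days". Unexposed time for each infusion is the gap minus the days the regimen allows, with a floor: "Time not exposed (days) is to be set to 0 days if the above derivation results in number of days less than 0". The allowed days are not defined separately. Adherence to the prophylactic dose (actual amount within 90% to 110% of planned) is a percentage formed "using the overall number of infusions for that subject as denominator", so its base is infusions received.

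SAP 4.4 lists possible major deviations for a meeting before database lock. One is "Subject less than 75% exposed to BAX 855 as derived in Section 6.8: Measurements of Treatment Compliance". The next is less than 75% compliance with the planned regimen, and no formula is attached to it. Listed items do not lead automatically to exclusion.

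Protocol 9.3 allows, but does not require, withdrawal of a subject who "misses more than 30% of planned prophylactic doses within any 3-month period".

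**The concern.** The rule allows a day more than the longest planned gap on every twice-weekly interval, while the every-5-day and every-7-day regimens get no tolerance. A twice-weekly subject who in practice doses every 5 days therefore looks the same as one who follows the schedule. No 6.8 measure would reveal this, because unexposed time cannot go below zero and dose adherence takes received infusions as its base.

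Two outputs are at stake. Compliance is summarized for the safety and per-protocol sets, and the figure would be wrong for under-dosed subjects. The 75% exposure item in SAP 4.4 takes its value from 6.8, so the measure affects who is brought to the meeting on the per-protocol set. SAP 7.1 reports the ABR models on that set as well as on the full analysis set.

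**Working it through.** The documents give no compliance figure to reproduce, so the 6.8 formulas are applied to stated dosing patterns.

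**Inputs**
- Planned mean interval: 3.5 days, or 2 infusions a week (Protocol 8.7.3.1).
- Schedule limit: 5 days (SAP 6.8).
- Allowed days in the exposure formula: 5. This is an assumption; SAP 6.8 implies it without stating it.
- Schedule score: share of infusions with a gap of at most 5 days.
- Time exposed: (OPE − Σ max(0, gap − 5)) / OPE.
- Share of planned doses missed at a constant gap g: 1 − 3.5/g.

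**Pattern A: every gap is 5 days**
- Infusions per week: 7/5 = 1.4 against 2 planned, so 1 − 3.5/5 = 30.0% are missed.
- Schedule score 100%. Unexposed days 0, so 100% exposed.
- In a 91-day window, 26 infusions are planned and 18 or 19 are given, depending on where the window starts. That is 8/26 = 30.8% or 7/26 = 26.9% missed. The long-run value is exactly 30%, at the Protocol 9.3 limit and not above it.

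**Pattern B: three 5-day gaps, then one 7-day gap, repeated**
- Cycle length 3 × 5 + 7 = 22 days, with 4 infusions given.
- Planned: 22/3.5 = 6.29. Missed: 1 − 4/6.29 = 36%.
- Schedule score: 3/4 = 75%. Time exposed: (22 − 2)/22 = 91%.
- Any 91-day window is four cycles (88 days, 16 infusions) plus 3 days that hold at most one more. So 16 or 17 of 26 are given and 38.5% or 34.6% are missed. Every 3-month window is above 30%.
- Neither score is below 75%.

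**Pattern C: 30% of doses omitted from a Monday/Thursday calendar**

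Per 20 planned doses (70 days), 6 are omitted and 14 given.

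| Omissions | Long gaps | On schedule | Exposed |
|---|---|---|---|
| Singly | 6 gaps of 7 days | 8/14 = 57% | (70 − 12)/70 = 83% |
| In pairs | 3 gaps of 10 or 11 days | 11/14 = 79% | (70 − 18)/70 = 74% to (70 − 15)/70 = 79% |
| In threes | 2 gaps of 14 days | 12/14 = 86% | (70 − 18)/70 = 74% |

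No skipping pattern here scores 100% on both measures. Some pairings stay at or above 75% on both.

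**Would a 4-day limit alone settle it?** Pattern A would score 0% on schedule but still 4/5 = 80% exposed, above the exposure trigger. Pattern B would score 0% on schedule and (22 − 3 × 1 − 3)/22 = 16/22 = 73% exposed.

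**Given over planned:** Pattern A scores 1.4/2 = 70% and Pattern B 4/6.29 = 64%. Both are below 75%.

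**The case against.** The strongest reply is that 5 days is a sensible tolerance. Under the protocol's late-dose rule, a Monday dose taken on Tuesday after a Thursday dose leaves a 5-day gap. In the bleed example in Protocol 8.7.3.1, a last therapeutic infusion on Wednesday followed by prophylaxis on Monday does the same. A flat 4-day limit would mark such protocol-permitted handling as non-adherent. This stands, and it is why the remedy should not rest on changing the constant. The SAP, however, does not describe the limit as a tolerance, and a tolerance applied to every interval still hides a 30% shortfall.

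It can also be said that under-dosing is visible elsewhere. SAP 6.7 derives average infusions per week by regimen, Protocol 10.7 has diaries reviewed for compliance, and SAP 4.4 provides for regular data review meetings. A reader of the listings could notice 1.4 infusions a week. Even so, no compliance measure or trigger uses that figure.

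A reader might infer more than the documents support:
- **That skipping 30% of doses scores 100%.** It does not. A single omitted calendar dose leaves a 7-day gap, which fails the rule and adds 2 unexposed days. The perfect score needs every interval stretched to 5 days.
- **That exposure stays acceptable up to 47.5% missed.** Exposure alone does stay at 75% up to a constant gap of 5/0.75 = 6.67 days (1 − 3.5/6.67 = 47.5% missed), but the schedule score is then 0%.
- **That a comparison with the every-5-day regimen is distorted.** SAP 5.7 and 7.1 model that regimen separately and specify no such comparison.

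**Conclusion.** The concern holds in this form: the 6.8 measures cannot detect a steady drift from twice-weekly to 5-day dosing. A subject 30% short of planned doses scores 100% on schedule and 100% exposed. A subject 36% short, above the Protocol 9.3 figure in every 3-month window, scores 75% and 91%. Neither subject falls below 75% on either measure.

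This rests on 5 being the allowed days in the exposure formula, and on reading the second 75% item in SAP 4.4 as the schedule score. If that item was meant as doses received over doses planned, both subjects would be flagged, but the SAP does not say so. The 100% refers to schedule and exposure; the separate 90% to 110% dose check still applies.

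It would go too far to say that such subjects remain in the per-protocol set, since SAP 4.4 leaves that to case-by-case judgment. It would also go too far to say that uniform 5-day dosing meets the withdrawal criterion: the long-run shortfall is exactly 30%, the criterion is more than 30%, and it is discretionary. The documents do not show how many subjects dose this way, so the effect on the per-protocol ABR is unknown. The change is worth making because it is cheap and corrects a compliance figure that misdescribes under-dosed subjects.

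**What to change.** 1. In SAP 6.8, add prophylactic infusions given divided by prophylactic infusions planned over the OPE, by regimen.
2. In SAP 4.4, define the item on less than 75% compliance with the planned regimen by that ratio. Long-run 5-day dosing on the twice-weekly regimen then scores 70% and comes up for discussion.
3. List for the per-protocol meeting every subject with more than 30% of planned doses missed in any 3-month period, so that the Protocol 9.3 figure is visible when membership is decided.
4. State the allowed days for each regimen. The 5-day limit may stay if the SAP says that it is the 4-day maximum plus one day of tolerance for late doses.

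No new data are needed. The cost is SAP wording and minor programming. The main work is a planned-dose count that allows for protocol-permitted interruptions (bleeds, visit washouts, time in the surgery study) and says whether recovery infusions at visits count as given. Reported compliance will fall somewhat, and a few more subjects will be discussed at the meeting.
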